11.4. Analysis Plan

A trial flow chart will be constructed, showing the number of children screened, enrolled and randomised, together with reasons for exclusion at each stage. Baseline characteristics of trial participants will be summarised by trial arm. Numbers and proportions will be reported for categorical characteristics. Means, standard deviations, medians and ranges will be used for continuous characteristics.

All trial analyses will be done using the intention-to-treat population, i.e. all children will be included as randomised, regardless of whether or not they received the allocated treatment. Children will contribute to 4 week outcomes if they are assessed within 1 week of the 4 week time point. Children will contribute to 6 and 12 month outcomes if they are assessed within 2 weeks of these time points. Since loss to follow-up is expected to be low at 4 weeks, only children for whom outcome data are available will be included in analyses (complete case analysis), with no imputation of missing outcome data planned.

The primary outcome of cure rate will be compared between trial arms using a chi-squared test statistic. The difference in proportions cured and a corresponding 95% confidence interval will be calculated. The related primary outcome, egg reduction rate, is defined as the percentage decrease in egg count between baseline and follow-up. The mean egg reduction rate will be compared between trial arms using a t-test, with the difference in mean egg reduction rate and its 95% confidence interval calculated. Schistosomal (CCA and CAA) antigenic egg clearance outcomes will be analyzed using the same approach as for cure rate (based on microscopy).

Prevalence of adverse events (both any and separately for types of event that occur with overall prevalence >5%) will be compared between trial arms using chi-squared tests. Rare adverse events will be tabulated by trial arm but no formal statistical comparisons done. Severity of adverse events will also be tabulated, by trial arm.

For the secondary outcomes assessed at 6 and 12 months (anthropometry and anemia), continuous outcomes will be compared between trial arms using linear regression, including the corresponding baseline measure as a covariate. Binary outcomes assessed at 6 and 12 months will be compared between trial arms using binary/logistic regression, including the corresponding baseline measure as a covariate. This will be done in order to improve the precision of the treatment effect estimate.

Due to the large sample size, no imbalance is expected between trial arms. Therefore, no further adjustment for baseline characteristics is planned for any outcome, unless there are significant differences demonstrated at baseline for key potential confounders.

We will pre-specify three key potential effect modifiers to be examined. These include site (Uganda versus the Philippines), age (12-30 months versus 31-47 months) and baseline intensity of infection (Low versus moderate/high). We will examine whether cure rate and egg reduction rate, as well as key measures of morbidity differ by these sub-groups. Effect modification will be tested by fitting interaction terms in regression models.

Full details, including shell tables will be included in a formal statistical analysis plan, to be finalized and reviewed before database lock.

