| Description of Study Design: | 
 1. Drug efficacy assessed by novel antigenic endpoints (CCA and CAA) among all children, and in relation to PK/PD parameters associated with cure (Area-Under-the Curve (AUC)) at 4 +/- 1 weeks post-PZQ in a subset of children. 2. 12 hour clinical monitoring for safety including active capture of adverse events and assessment of toxicity through serum chemistries and hematologic parameters. 3. Iron status, hemoglobin, and age and gender adjusted longitudinal growth and nutritional status 4. Biomarkers of inflammation and EE including fecal calprotectin, urine lactulose:mannitol ratio, serum endotoxin, serum endotoxin core antibody, and proinflammatory cytokines 5. Inter-individual variability in PZQ AUC as modified by Environmental Enteric Dysfunction (EED) 6. Immune responses to S. mansoni infection and treatment 7. Prevalence and the pattern of schistosomiasis-related morbidity as determined by ultrasound scan. 
Four parallel arm randomized quasi-double blinded placebo-controlled trial with a 4 week, 6 months and 12 month follow up. Interventions will be given at baseline and at 6 months. Parasitological endpoints will be measured at 4 weeks. Morbidity endpoints will be measured at 6 and 12 months.
 |
| Estimated Time to Complete Enrolment: | 24 months |

Table 1: Treatment Arms*

| | Number of subjects | Baseline Dose | 6 months post baseline dose |
|-------|--------------------|---|---|
| ARM 1 | 150 | 40 mg/kg dose PZQ (40 mg/kg followed by Placebo 3 hours later) | Placebo followed by Placebo 3 hours later |
| ARM 2 | 150 | 40 mg/kg dose PZQ (40 mg/kg followed by Placebo 3 hours later) | 40 mg/kg dose (40 mg/kg followed by Placebo 3 hours later) |
| ARM 3 | 150 | 80 mg/kg split dose PZQ (40 mg/kg followed by 40 mg/kg 3 hours later) | Placebo followed by Placebo 3 hours later |
| ARM 4 | 150 | 80 mg/kg split dose PZQ (40 mg/kg followed by 40 mg/kg 3 hours later) | 80 mg/kg split dose (40 mg/kg followed by 40 mg/kg 3 hours later) |

*** These numbers represent subject totals across both sites. At each site, approximately N=75 subjects will be enrolled in each of the 4 arms providing N=300 subjects at each site.**

Figure 1: Schematic of Study design

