11.2. Sample Size Considerations

The sample size calculations are based on the primary outcome of cure rate at 4 weeks. Cure rate is defined as the proportion of individuals who are uninfected at the follow-up, where infection will be assessed using parasitological methods. The null hypothesis is that cure rate at 4 weeks is the same between children who received 40 mg/kg praziquantel and children who received 80 mg/kg praziquantel. The null hypothesis will be tested using a chi-squared test statistic. The analysis population will be comprised of all participants as randomised, regardless of whether or not they received the allocated treatment (intention-to-treat).

Data from Uganda found cure rates for *S. mansoni* infected 3-9 year olds of 70% and 82% for 40 mg/kg and 60 mg/kg praziquantel, respectively. We anticipate that cure rates may be lower in younger children and that the 80 mg/kg dose will have a higher cure rate than the 60 mg/kg. However, we conservatively power the trial to detect a difference in cure rate of 70% versus 82%. Using a two-sided 5% significance level, approximately 173 children per trial arm will be required for 80% power and 232 per arm (N=464) for 90% power to detect a difference in cure rate at 4 weeks between the trial arms. Allowing for loss to follow-up of 7%, a total of approximately 500 children will be required. A sample size of 600 will allow us adequate power to examine sub-groups such as younger (12-30 months) versus older (30-47 months) children, particularly given that the effect size is likely to be larger based on a higher dose (80 mg/kg).

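### The primary cure-rate test is valid but leaves out site, baseline egg intensity and age, and covariates can enter only through a chance-triggered baseline test

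*Combined protocol and SAP*

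**What the plan says.** The primary analysis is given in Section 11.4: "The primary outcome of cure rate will be compared between trial arms using a chi-squared test statistic", with a difference in proportions and its 95% CI. Section 11.2 bases the sample size on the same test. Neither section puts a covariate or stratum into the primary comparison.

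On baseline covariates, Section 11.4 expects no imbalance because the trial is large, and then says that "no further adjustment for baseline characteristics is planned for any outcome, unless there are significant differences demonstrated at baseline for key potential confounders". It does not list the confounders, the baseline test, the significance threshold or the model that would replace the chi-squared test.

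The same section does two other things that bear on this:
- It adjusts the 6- and 12-month outcomes for their own baseline value and gives precision as the reason.
- It pre-specifies site, age group and baseline intensity (low versus moderate/high) as effect modifiers for cure rate, but uses them only in interaction tests.

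On allocation, the footnote to Table 1 in the Protocol Summary says "At each site, approximately N=75 subjects will be enrolled in each of the 4 arms". Section 5.3.1 describes randomly permuted blocks and names no stratification factor.

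**The concern.** The documents give reasons to expect these factors to predict cure. Site separates *S. mansoni* from *S. japonicum* (Sections 4.2.1 and 5.1). The number of baseline stool samples differs by site (Section 7.2). Section 11.2 expects younger children to be cured less often. Egg intensity is measured before treatment. The plan accepts the precision argument for the later outcomes but does not apply it to the primary one.

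The conditional clause is the weaker part of the plan. In a randomised trial a significant baseline difference arises by chance, so the clause lets chance decide whether the primary model is adjusted. Because covariates, threshold and model are all open, it also leaves room to choose after seeing data. If the logistic regression planned for later binary outcomes were taken over, the primary result could change from a risk difference to an odds ratio.

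At stake are some precision and the firmness of the pre-specification. The validity of the primary test is not at stake.

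**Working it through.** **1. The plan's own figures.** Section 11.2 says "Using a two-sided 5% significance level, approximately 173 children per trial arm will be required for 80% power and 232 per arm (N=464"), for an effect described as "we conservatively power the trial to detect a difference in cure rate of 70% versus 82"%. The pooled two-proportion formula is

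n = [1.96·√(2·0.76·0.24) + z·√(0.70·0.30 + 0.82·0.18)]² / 0.12²

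- 80% power: (1.960·0.6040 + 0.8416·0.5980)² / 0.0144 = 197.7, so 198 per group.
- 90% power: (1.960·0.6040 + 1.2816·0.5980)² / 0.0144 = 264.1, so 265 per group.

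The stated 173 and 232 do not reproduce; at 70% v 82% they give 74.5% and 85.9% power. That is a separate matter. Its only bearing here is that 2 × 265 = 530, and 530/0.93 = 570, which is below the planned 600.

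**2. Power of the planned test at 600.** With the 7% loss in Section 11.2, 600 × 0.93 = 558, or 279 per dose group.

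- SE under the null: √(2·0.76·0.24/279) = 0.0362
- SE under the alternative: √(0.3576/279) = 0.0358
- z = (0.12 − 1.96·0.0362)/0.0358 = 1.37, so power is 91.5%.

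**3. Chance of triggering the clause.** For k independent baseline tests at 5%, the chance of at least one positive is 1 − 0.95^k: 14% for k = 3, 23% for k = 5, 40% for k = 10. Neither k nor the 5% threshold is in the documents.

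**4. What adjustment would gain.** The documents give no prognostic strength, so the odds ratios below, and 40% of children at moderate/high intensity, are assumptions. Simulation: 100,000 trials per row, 279 per dose group, overall cure 70% v 82%, dose groups balanced within site. The adjusted test is Cochran-Mantel-Haenszel (CMH), stratified by site × intensity. The clause column uses CMH only if the intensity imbalance has p < 0.05, and chi-squared otherwise. The last column is the variance of the unadjusted risk difference divided by that of the stratified one.

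| Odds ratios (site, intensity) | Power, chi-squared | Power, CMH | Power, clause | Variance ratio |
|---|---|---|---|---|
| none | 91.7% | 91.5% | 91.7% | 1.00 |
| 1.5, 2 | 91.8% | 92.3% | 91.9% | 1.02 |
| 2, 3 | 91.8% | 93.2% | 92.0% | 1.05 |
| 3, 4 | 92.1% | 94.4% | 92.4% | 1.08 |
| 4, 6 | 92.4% | 95.8% | 92.8% | 1.15 |

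Planned adjustment changes power by −0.2 to +3.4 points. In the strongest row the clause recovers 0.4 of those 3.4 points. As sample size, the ratios 1.02 and 1.15 correspond to 558 × 1.02 = 569 and 558 × 1.15 = 642 evaluable children, that is 11 and 84 more. If the dose groups are not balanced within site, the largest ratio is about 1.22.

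A separate simulation (3,000 trials per scenario) adjusted for site and log baseline egg count. It assumed a site log-odds ratio of 0.6 to 1.0 and −0.5 to −1.0 per SD of log count. The adjusted variance was 0.947 to 0.835 of the unadjusted. It had no weak or null scenario, so it shows only the upper part of the range.

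**5. Type I error, same simulation as the table.** From the no-effect row to the strongest:
- chi-squared: 5.1% down to 4.1%
- CMH: 4.8% to 5.0% throughout
- clause followed strictly: 5.1% down to 3.8% (4.8% to 3.8% in the four prognostic rows)
- smaller of the two p-values: 5.3% up to 6.2%

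**The case against.** The strongest defence is that nothing here is an error. An unadjusted chi-squared test with a risk difference is valid in a randomised trial, the sample size rests on it, and at 279 per group it has about 91.5% power. That stands. A reader might infer that the primary conclusion is in danger; it is not.

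A reader might also infer that the standard error is too large. That holds only if site or intensity predicts cure, and the documents do not say how strongly either does. If neither does, adjustment costs about 0.2 points of power. Nor do the documents establish randomisation stratified by site: Section 5.3.1 names no factor, and the Table 1 footnote gives an approximate number per site.

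A third tempting reading is that the clause inflates type I error, or that it would fire 40% of the time. Followed strictly for intensity, it does not inflate the error. The 40% needs ten tests, which appear nowhere; Section 11.4 names three key baseline factors, and three tests give 14%.

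The clause also has an understandable purpose, since a chance imbalance in a strong predictor does distort the unadjusted result in that particular trial. Planned adjustment handles this without a trigger.

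Finally, Section 11.4 defers full details to a formal SAP before database lock. That would answer a silence, but here the protocol states a rule, and the rule has to be replaced. Database lock is also late: Section 11.3.1 unblinds the trial statistician for an interim analysis of the primary outcome at about 20% randomised.

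**Conclusion.** The point holds as a recommended improvement. The primary test is sound, but it does not use covariates that the plan itself treats as important for cure rate. The clause on baseline differences lets chance alter the model for almost no benefit.

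The size is modest: about −0.2 to +3.4 power points from a base near 91.5%, and an unadjusted variance 0 to 15% larger with dose groups balanced within site. All of this rests on assumed odds ratios, an assumed 40% at moderate/high intensity, and the plan's 70% v 82% and 7% loss. The trigger probability, 14% to 40%, rests on an assumed number of independent tests at 5%. Excess type I error, to about 6%, would arise only if the more favourable of two analyses were chosen, which the open wording of the clause does not prevent.

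**What to change.** Before any unblinded look at the primary outcome, including the 20% interim analysis:

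1. Make the primary analysis a pre-specified adjusted risk difference with 95% CI. Choose one of two forms in advance: Mantel-Haenszel stratified by site and baseline intensity (low v moderate/high), or a risk difference standardised from a logistic model with dose, site, log baseline egg count and age.
2. Keep the plain chi-squared test as a sensitivity analysis.
3. Delete the clause that makes adjustment depend on significant baseline differences.
4. For the 6- and 12-month outcomes, keep the outcome-specific baseline value already planned and add site. Do not replace that value with a common covariate set, which could lose precision.
5. State in Section 5.3.1 whether randomisation is stratified by site.

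Cost: the chi-squared test is protocol text (Sections 11.2 and 11.4), so this needs a short amendment with IRB/IEC approval under Section 14.2 as well as SAP wording, and slightly more analysis work. If the covariates turn out not to predict cure, the power loss is negligible.

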3.2. Study Outcome Measures

3.2.1. Primary

To measure **drug efficacy** as per standard parasitological endpoints including a) Cure Rate as defined by the proportion of children who have zero eggs per gram of stool as assessed by Kato-Katz four weeks following treatment and b) Egg reduction Rate as defined by the percent reduction in egg burden from baseline to four weeks post treatment as assessed by Kato-Katz.

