11. STATISTICAL CONSIDERATIONS

11.1. Study Hypotheses

Primary outcome

The null hypothesis that there is no difference in cure rate assessed by microscopy at 4 weeks between children who received 40 mg/kg praziquantel and children who received 80 mg/kg praziquantel. This will be tested against the alternative hypothesis that there is a difference in cure rate at 4 weeks between children who received 40 mg/kg praziquantel and children who received 80 mg/kg praziquantel, and will be a superiority comparison.

Secondary outcomes

All secondary outcomes will be superiority comparisons, with alternative hypothesis of a difference in the outcome between the two sets of participants being compared.

For outcomes 1 to 5 below, the null hypothesis is that there is no difference in the outcome between children in the 40 mg/kg praziquantel group and children in the 80 mg/kg praziquantel group.

1. Mean egg reduction rate at 4 weeks
2. Schistosomal antigenic clearance assessed by CCA at 4 weeks
3. Schistosomal antigenic clearance assessed by CAA at 4 weeks
4. Prevalence of any adverse event within 3 hours of dosing

Adverse events will be classified by type. Adverse event types that occur with overall prevalence >5% or at prevalence >5% in either setting will also be tested for differences between trial arms.

5. (a) Prevalence of adverse event type 1 within 3 hours of dosing
(b) Prevalence of adverse event type 2 within 3 hours of dosing
(c) Prevalence of adverse event type 3 within 3 hours of dosing
continued for all adverse event types occurring with prevalence >5%

For secondary outcomes 6 to 13 below, two null hypotheses will be tested. The first null hypothesis is that there is no difference in the morbidity outcomes between children who received six-monthly praziquantel (either 40 mg/kg or 80 mg/kg) and children who received 12-monthly praziquantel (either 40 mg/kg or 80 mg/kg). The second null hypothesis is that there is no difference in the morbidity outcomes between children who received 40 mg/kg praziquantel (regardless of dosing schedule) and children who received 80 mg/kg praziquantel (regardless of dosing schedule).

6. Mean weight-for-height z-score at 12 months
7. Proportion with weight-for-height z-score at 12 months < -2
8. Mean MUAC-for-age z-score at 12 months
9. Proportion with MUAC-for-age z-score at 12 months < -2
10. Mean height-for-age z-score at 12 months
11. Proportion with height-for-age z-score at 12 months < -2

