11.3. Planned Interim Analyses

11.3.1. Interim Safety Review

Given that the study population is vulnerable the project will require rigorous independent oversight by a data safety and monitoring board (DSMB). DSMB membership will be independent of the trial with input from investigators; we anticipate that it will comprise experts on schistosomiasis and child health, and a statistician with experience of trials in LMICs. The frequency of meetings and other procedural issues will be overseen by the study sponsor.

The DSMB will regularly monitor all data to consider any potential harm to participants. Formal rules for stopping due to harm will be discussed with the DSMB at their first meeting. An interim analysis will be performed on the primary outcome when approximately 20% of children have been randomised. Only the DSMB and the trial statistician will be unblinded for this interim analysis.

The DSMB will meet once three months after study enrollment begins and then every six months during enrollment.

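### Egg reduction rate is primary in four places and the first secondary outcome in a fifth, with no rule for success, and the 20% interim look at the primary outcome has no stated purpose or boundary

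*Combined protocol and SAP*

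**What the plan says.** **Status of ERR.** Section 3.2.1 lists cure rate as primary outcome a) and then "b) Egg reduction Rate as defined by the percent reduction in egg burden from baseline to four weeks post treatment". The Protocol Summary and 3.1.1 pair the two outcomes in the same way. Section 11.4 calls ERR "The related primary outcome, egg reduction rate" and assigns it a t-test. Section 11.1 states the primary hypothesis for cure rate alone and puts "Mean egg reduction rate at 4 weeks" first among the secondary outcomes. Section 11.2 sizes the trial on cure rate alone: "Using a two-sided 5% significance level, approximately 173 children per trial arm will be required for 80% power". Its figure at the higher power level is "232 per arm (N=464) for 90% power".

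**Interim look.** Section 11.3.1, headed as a safety review, says: "An interim analysis will be performed on the primary outcome when approximately 20% of children have been randomised". It continues: "Only the DSMB and the trial statistician will be unblinded for this interim analysis". It gives no test, significance level, boundary or alpha spending, and does not say that the look is without consequence for efficacy. The only stopping rules it mentions concern harm, and these are left for discussion with the DSMB.

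**SAP timing and blinding.** Section 11.4 defers full details to a formal SAP, "to be finalized and reviewed before database lock". Section 15.4 says that all analysis will be completed while the treatment code is still unbroken.

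**The concern.** Sections 11.1 and 11.4 cannot both be right about ERR. As written, a significant result on either outcome could be presented as success on a primary outcome, each tested at 5%, and no multiplicity rule prevents it. The ambiguity carries into the interim: with the primary outcome unsettled, it is unclear which outcome will be analysed by arm at 20%.

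Timing makes this worse. The trial statistician is unblinded at the interim, while the SAP need only be final by database lock. Two choices are then still open: the status of ERR, and covariate adjustment, which 11.4 makes depend on significant baseline differences in confounders that it does not name. The background section says that the trial is meant to support a labelling change. A primary outcome settled after the statistician had seen arm-level results would be hard to defend.

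**Working it through.** **Inputs from the documents.** Two-sided 5% level; cure rates 70% and 82%; 7% loss at 4 weeks (11.2). N = 600, with arms 1+2 against arms 3+4, so 300 per dose (Table 1). After loss: 600 × 0.93 = 558, or 279 per dose. Interim at about 20% randomised (11.3.1).

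**Assumptions not in the documents.** The correlation between the cure-rate and ERR test statistics is not given. A cured child has an ERR of 100%, so it should be positive; the range is shown. Interim information is taken as 0.2.

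**Step 1: the plan's own sample size.** n per dose = [z(α/2)·√(2p̄q̄) + z(β)·√(p₁q₁ + p₂q₂)]² / (p₂ − p₁)².

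- p̄ = 0.76, so √(2 × 0.76 × 0.24) = 0.604; √(0.21 + 0.1476) = 0.598; (0.12)² = 0.0144.
- 80% power: (1.960 × 0.604 + 0.842 × 0.598)² / 0.0144 = 197.7, so 198.
- 90% power: (1.960 × 0.604 + 1.282 × 0.598)² / 0.0144 = 264.1, so 265.

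The stated 173 and 232 do not reproduce at a two-sided 5% level. The closest match found is a one-sided 5% test with continuity correction (172 and 232). This is a separate matter: at 279 per dose, two-sided power is 91.5%, and that is the baseline used in step 5.

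**Step 2: two outcomes at the final analysis, either sufficient.** Error = 1 − P(|Z₁| ≤ 1.96 and |Z₂| ≤ 1.96), bivariate normal.

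- Correlation 0: 1 − 0.95² = 9.75%.
- Correlation 0.5: 9.1%.
- Correlation 0.8: 7.8%.

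If both must be significant, the error is at most 5%. If cure rate is the sole primary, it is 5%.

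**Step 3: cure rate at two looks, each at 5%, success possible at either.** The correlation between looks is √0.2 = 0.447, which gives 9.2%. With no efficacy decision at the interim, the figure is 5.0%.

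**Step 4: cure rate at both looks plus ERR at the final, any one sufficient.** At correlation 0: 1 − (1 − 0.0921) × 0.95 = 13.75%. Simulation (4 million draws) gives the rest.

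| Correlation, cure rate and ERR | Final only, either wins | Adding a 5% interim test of cure rate |
|---|---|---|
| 0 | 9.75% | 13.75% |
| 0.5 | 9.1% | 13.1% |
| 0.7 | 8.4% | 12.3% |
| 0.8 | 7.8% | 11.8% |

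Illustrative null data (70% cured, ERR = 100% if cured) gave a correlation of about 0.82 to 0.83 and an error of 11.8% to 11.9% when ERR in uncured children was bounded. With skewed ERR they gave a correlation of 0.36 and an error of 12.4%.

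**Step 5: what the remedies give.**

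- Cure rate as sole primary, no efficacy decision at the interim: 5.0%.
- Interim p < 0.001 with the final test at 0.05: 5.07%. With the final test at p < 0.0493: 5.0%.
- Two primaries at 0.025 each, final analysis only: at most 1 − 0.975² = 4.94%. Cure-rate power at 279 per dose: (0.12 × √279 − 2.241 × 0.604) / 0.598 = 1.088, so 86.2%, against 91.5% at 0.05.

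**The case against.** The strongest reply is that the protocol never describes an efficacy test at 20%. Section 11.3.1 sits under a safety heading, speaks of harm, and mentions stopping rules for harm only. Section 9.6.2 lets the DSMB recommend continuing, changing or ending the trial, but as a general statement about safety oversight. A look that supports no efficacy claim adds no type I error. This stands. A reader might infer that cure rate is tested unadjusted at the interim, or that the false-positive rate is about 13%. The documents do not support either as a statement of fact. The 13% figure needs a 5% interim test, success declarable there, a win on either outcome to count, and low to moderate correlation; none of these is stated. Nor does any text allow the sponsor to claim success at the interim, since unblinding is confined to the DSMB and the trial statistician.

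The second reply is that the analysis is not wide open. Sections 11.1 to 11.4 already fix the cure-rate hypothesis, the chi-squared test, the t-test for ERR, the intention-to-treat set, the assessment windows, the complete-case rule and three effect modifiers. A deadline of database lock also does not mean that the SAP will be unsigned at the interim. This too largely stands, and makes the timing point secondary. It does not settle the status of ERR or the conditional covariate adjustment.

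Neither reply touches the contradiction over ERR. It is in the text, and neither redaction nor PDF conversion explains it.

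**Conclusion.** The contradiction over ERR is established and should be fixed before any unblinded look. Its effect on the false-positive rate depends on a success rule that the plan does not give: 5% if cure rate is the sole primary, no more than 5% if both outcomes must succeed, and about 7.8% to 9.75% (correlation 0.8 to 0) if either suffices. The interim analysis is unspecified; it has not been shown to be a second test. It contributes nothing if it carries no efficacy decision. Only if efficacy could be declared there at 5%, and either outcome counted, would the total be roughly 12% to 14%. That is a conditional upper range under readings that the plan does not exclude, not the trial's error rate. The SAP date, and the conflict between 11.3.1 and 15.4 over when the code is broken, are real but lesser points.

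**What to change.** 1. Make cure rate the single primary outcome in the Protocol Summary, 3.1.1, 3.2.1 and 11.4, matching 11.1 and 11.2. Make ERR the first secondary outcome, tested only if cure rate is significant. Cost: ERR loses primary status. If the sponsor prefers two primaries with either sufficing, test each at 0.025; cure-rate power at 279 per dose then falls from 91.5% to 86.2%. If both must succeed, say so; no alpha adjustment between the two outcomes is then needed.
2. State in 11.3.1 that the 20% look carries no efficacy decision. If it is to carry one, use p < 0.001 at the interim and about p < 0.0493 at the final analysis.
3. Finalise the SAP before the interim unblinding, not only before database lock, with the baseline covariates for any adjustment named.
4. Reconcile 11.3.1, which unblinds the trial statistician at the interim, with 15.4, which has all analysis done before the code is broken.

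Items 1 to 4 need protocol and SAP wording and an earlier SAP sign-off date. They do not change the planned 600 children or any study procedure.
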